6.4 Pharmacokinetic Concentrations

Plasma concentrations of xisomab 3G3 as determined at the collection times and per the bioanalytical method described in Section 6.1 and Section 6.2, respectively, will be used for the calculation of the plasma xisomab 3G3 PK parameters.

6.5 Noncompartmental Pharmacokinetic Analysis and Parameter Calculation

6.5.1 Plasma Pharmacokinetic Parameters

The appropriate noncompartmental PK parameters will be calculated from the plasma xisomab 3G3 concentration-time data using Phoenix WinNonlin Version 6.3 or higher. Actual sample times will be used in the calculations of the PK parameters. The calculation of the actual time for xisomab 3G3 will be in respect to the start of infusion time of xisomab 3G3 on Day 1. All PK parameters included in the protocol are listed in Table 6.1 below, and are defined as appropriate for study design.

Table 6.1. Noncompartmental Pharmacokinetic Parameters to be Calculated

Parameter	Label to be Used in the Text, Tables and Figures	Definition	Method of Determination
AUC _{0-t}	AUC0-t	Area under the concentration-time curve from time 0 to the time of the last measurable non-zero concentration	Calculated using the Linear Trapezoidal with Linear Interpolation Method
AUC _{0-inf}	AUC0-inf	Area under the concentration-time curve from time 0 extrapolated to infinity	AUC0-inf = AUC0-t + (Clast/kel) where Clast is the last observed/measured concentration
AUC _{%extrap}	AUC%extrap	Percent of AUC0-inf extrapolated	AUC%extrap = (1 - AUC0-t/AUC0-inf)*100
AUMC _{0-inf} *	AUMC0-inf	Area under the moment curve from time 0 extrapolated to infinity	AUMC0-inf = AUMC0-t + [(tlast x Clast)/ Kel]+ [Clast/(Kel) ²]
C_{max}	Cmax	The maximum observed concentration	Taken directly from bioanalytical data
T _{max}	Tmax	The time to reach Cmax. If the maximum value occurs at more than one time point, Tmax is defined as the first time point with this value	Taken from clinical database as the difference in the start time of the infusion and the time of the blood draw which is associated with the Cmax.
K _{el}	Kel	Apparent first-order terminal elimination rate constant calculated from a semi-log plot of the plasma concentration versus time curve	The parameter will be calculated by linear least-squares regression analysis using the maximum number of points in the terminal log-linear phase (e.g., three or more non-zero plasma concentrations).

Parameter	Label to be Used in the Text, Tables and Figures	Definition	Method of Determination
T _{1/2}	T1/2	Apparent first-order terminal elimination half-life	Calculated as: 0.693/ Kel
CL	CL	The apparent total plasma clearance after IV administration	Calculated as: Dose/(AUC0-inf)
MRT *	MRT	Mean residence time of unchanged drug in the systemic circulation when the drug concentrations are extrapolated to infinity	Calculated as: (AUMC0-inf/AUC0-inf) – (TI/2) Where TI is the duration of infusion
V _{ss}	Vss	Total apparent volume of distribution following single IV dose administration	Calculated as: MRT x CL

^{*} AUMC0-inf and MRT values will be used for Vss calculation but will not be listed in the PK tables.

* Note for the programmer: Parameters which are calculated for use in the calculation of a separate

PK parameters will not be calculated for subjects with less than 3 consecutive postdose time points with quantifiable concentrations. Subjects for whom there are insufficient data to calculate the PK parameters will be included in the concentration tables only and excluded from the statistical analysis.

For the calculation of the PK parameters, plasma concentrations below the limit of quantitation (BLQ) prior to the first quantifiable concentration will be set to 0 and plasma concentrations BLQ after the first quantifiable concentration will be treated as missing.

The Kel will be determined using linear regressions composed of least 3 data points. The Kel will not be assigned if 1) the terminal elimination phase is not apparent, 2) if Tmax is one of the 3 last data points, or 3) if the R² value is less than 0.8. In cases where the Kel interval is not assigned, the values of AUC0-inf, AUC%extrap, AUMC0-inf, T1/2, CL, MRT, and Vss are considered not calculable and will not be reported. Wherever the resulting T1/2 is more than half as long as the sampling interval, the Kel values and associated parameters (AUC0-inf, AUC%extrap, AUMC0-inf, T1/2, CL, MRT, and Vss) may not be presented as judged appropriate and in accordance with Celerion SOPs.

^{*} Note for the programmer: Parameters which are calculated for use in the calculation of a separate parameter but that are not summarized in the PK tables (i.e., AUMC0-inf and MRT) will be included in the study data tabulation model (SDTM) PP(Pharmacokinetic Parameters) domain, but not included in the analysis data model (ADaM) ADPP (Pharmacokinetic Parameters Analysis) domain.

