The goal of xisomab 3G3 treatment is to achieve safe anticoagulation for several days with a single dose. A single dose of xisomab 3G3 demonstrated potent and sustained antithrombotic effects in both mice and nonhuman primate models, and showed no toxicity at and above saturating doses in nonclinical Good laboratory Practice (GLP) toxicity studies in rats and cynomolgus monkeys. Saturation of binding to the molecular target and the maximum FXI inhibitory effect is achieved at a relatively low dose of xisomab 3G3 because FXI circulates at a low plasma concentration (3 to 10 mg/L), and the antibody has high affinity toward FXI. The effect of increasing the dose above the saturating level results in prolongation of

anticoagulation in a dose-dependent manner. Since there has been no observed toxicity associated with a dose more than 50-fold over the predicted effective target dose in humans as determined by GLP toxicity studies in both rats and nonhuman primates, the therapeutic index is expected to be very high.

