#### **12.1.4 Pharmacokinetic Analysis**

##### **12.1.4.1 Pharmacokinetic Parameters**

The following PK parameters will be computed, as appropriate, for plasma free xisomab 3G3 from the individual plasma concentrations using a noncompartmental approach.

AUC0-t: The area under the plasma concentration-time curve, from time 0 to the last measurable non-zero concentration, as calculated by the linear trapezoidal method.

AUC0-inf: The area under the plasma concentration-time curve from time 0 extrapolated to infinity. AUC0-inf is calculated as the sum of AUC0-t plus the ratio of the last measurable plasma concentration to the elimination rate constant.

---

AUC% extrap :	Percent of AUC 0-inf extrapolated, represented as $(1 - AUC_{0-t}/AUC_{0-inf}) * 100$ .
AUMC 0-inf *:	Area under the moment curve from time 0 to the last measurable concentration, = AUMC 0-t + [(t last x C t ) / K el ] + C t / (K el ) 
C max :	Maximum observed concentration.
T max :	Time to reach C max . If the maximum value occurs at more than one time point, T max is defined as the first time point with this value.
K el :	Apparent first-order terminal elimination rate constant calculated from a semi-log plot of the plasma concentration versus time curve. The parameter will be calculated by linear least-squares regression analysis using the maximum number of points in the terminal log-linear phase (e.g., three or more non-zero plasma concentrations).
T ½ :	Apparent first-order terminal elimination half-life will be calculated as 0.693 / K el .
CL:	Apparent total plasma clearance calculated as [Dose / AUC 0-inf ].
MRT:*	Mean residence time = AUMC 0-inf / AUC 0-inf (for IV infusion)
V ss :	Total apparent volume of distribution following single IV dose administration calculated as V ss = MRT x CL.

\* AUMC0-inf and MRT values will be used for Vss calculation but will not be listed in the PK tables.

Additional PK parameters may be computed if deemed appropriate.

No PK parameters will be calculated for subjects with 2 or fewer consecutive time points with detectable concentrations.

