4. ANALYSIS POPULATIONS

4.1 Analysis Populations

Safety Population

The safety population will include all subjects who received at least one dose of study drug (active or placebo).

Pharmacokinetic Population

The PK population will include data from all subjects who received at least one dose of active study drug and completed at least one PK blood draw resulting in at least one quantifiable plasma concentration. Samples from all subjects will be assayed even if the subjects do not complete the study. All subjects who comply sufficiently with the protocol and display an evaluable PK profile (e.g., exposure to treatment, availability of measurements and absence of major protocol violations) will be included in the PK parameter summary and statistical analyses.

Pharmacodynamic Population

The PD population will include all subjects who received the study drug (active or placebo) and have at least one predose and one postdose quantifiable PD biomarker value. All subjects who comply sufficiently with the protocol and display an evaluable PD profile will be used for summary statistics.

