6.2 Bioanalytical Method

Plasma concentrations of xisomab 3G3 will be determined using enzyme-linked immunosorbent assay (ELISA) validated with respect to accuracy, precision, linearity, sensitivity, and specificity at Celerion, Lincoln, Nebraska. The analytical range (lower limit of quantitation [LLOQ] – upper limit of quantitation [ULOQ]) for xisomab 3G3 is expected to be 50 – 5000 ng/mL.

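### The three-sample rule withholds Cmax and Tmax along with the Kel-dependent parameters, and could bias Cohort 1 Cmax and AUC0-t upward if free drug lies near the assay limit

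*SAP*

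**What the plan says.** SAP 6.5.1: "PK parameters will not be calculated for subjects with less than 3 consecutive postdose time points with quantifiable concentrations". Such subjects "will be included in the concentration tables only and excluded from the statistical analysis". Protocol 12.1.4.1 is nearly the same but uses a different term: "No PK parameters will be calculated for subjects with 2 or fewer consecutive time points with detectable concentrations". Neither text exempts any parameter.

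Four other provisions bear on this:

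- **Cmax and Tmax.** SAP Table 6.1 gives the source of Cmax as "Taken directly from bioanalytical data". Tmax is the time of that same sample. Neither involves a fit.
- **Kel.** SAP 6.5.1 separately requires at least three points for the Kel regression. If Kel cannot be assigned, only AUC0-inf, AUC%extrap, AUMC0-inf, T1/2, CL, MRT and Vss are withheld.
- **PK population.** SAP 4.1 admits an actively dosed subject who "completed at least one PK blood draw resulting in at least one quantifiable plasma concentration".
- **Assay range.** SAP 6.2 says that it "is expected to be 50 – 5000 ng/mL".

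**The concern.** The Kel rule already protects the parameters that need a terminal slope. What the blanket rule adds is the loss of the parameters that need no slope: Cmax, Tmax and AUC0-t. When it is triggered by low concentrations, it selects subjects on the quantity being summarised, so the Cmax and AUC0-t summaries of those who remain can only move upward. No direction follows for Tmax.

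Cohort 1 is the likeliest place for this. The analyte is free antibody, and Protocol 8.2 notes that "FXI circulates at a low plasma concentration (3 to 10 mg/L", with high antibody affinity. At 0.1 mg/kg there may be less antibody than target, which could leave little of it free. With four active subjects, losing one removes a quarter of the low-dose summary. Protocol 8.4.1 wants the study to inform Phase 2 dose levels and intervals, and Protocol 10.4.1.4 lets PK guide escalation.

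**Working it through.** The plan gives no figure to reproduce: no predicted human free concentration, no binding constant and no expected number of exclusions. Three checks were made.

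**1. Linear scaling from the baboon data (Protocol 8.3.2).** Dose-normalised free Cmax is 19.66. The printed unit is L/kg; it is read here as kg/L, since 1/0.050 L/kg = 20 kg/L.

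- Cmax at 0.1 mg/kg = 0.1 × 19.66 = 1.966 mg/L = 1,966 ng/mL. This is 1,966/50 = 39 times the lower limit, or log2(39.3) = 5.30 half-lives above it.
- At the baboon half-life of 45 to 75 h, levels stay quantifiable for 5.30 × 45 = 238 h to 5.30 × 75 = 397 h. That covers 11 to 12 of the 14 scheduled postdose samples.
- To trigger the rule, the third sample (0.5 h) would have to be below 50 ng/mL, which needs a half-life of 0.5/5.30 = 0.09 h.

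On this reading nobody is excluded at any dose.

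**2. Target binding.** Taking 0.050 L/kg as the volume, total antibody T = 0.1/0.050 = 2 mg/L, against FXI of 3 to 10 mg/L. For 1:1 binding with capacity B and dissociation constant K:

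free = [(T − B − K) + √((T − B − K)² + 4KT)] / 2

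K and the binding ratio are not in the documents. Assumed: K = 0.015 to 1.5 mg/L, and 0.5 to 2 mg of antibody bound per mg of FXI.

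- Low end (B = 10 × 2 = 20, K = 0.015): [−18.015 + √(324.54 + 0.12)]/2 = 0.0017 mg/L, about 2 ng/mL.
- High end (B = 3 × 0.5 = 1.5, K = 1.5): [−1.0 + √(1 + 12)]/2 = 1.30 mg/L, about 1,300 ng/mL.

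The range straddles 50 ng/mL. At 0.5 mg/kg only the most extreme combination falls below it (15 ng/mL). At 2 and 5 mg/kg free drug is at least 20,000 ng/mL.

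**3. Simulated effect of the rule.** 200,000 subjects, sampled at 0.083 to 72 h, with a 50 ng/mL limit. Assumed: lognormal peak with CV 50%, 15% noise per sample, half-life 1.3 to 45 h, and a value below the limit breaks a run. The last column is the separate inflation from dosed subjects with no quantifiable sample, who never enter the PK population.

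| Median free Cmax (ng/mL) | Some quantifiable data, no Cmax | At least 1 of 4 lost | Inflation of geometric mean Cmax from the rule | Inflation from subjects with no quantifiable sample |
|---|---|---|---|---|
| 60 | 17–26% | 52–69% | 12–19% | 21–32% |
| 100 | 6–14% | 22–46% | 5–10% | 4–8% |
| 200 | about 1% or less | up to about 4% | about 1% or less | – |
| about 2,000 | none | none | none | none |

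The third column is 1 − (1 − p)⁴, with p the unrounded share lost; for example, 1 − (1 − 0.01)⁴ = 4%.

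The two inflations multiply. At 60 ng/mL the total is 1.12 × 1.21 = 1.36 to 1.19 × 1.32 = 1.57. At 100 ng/mL it is 1.05 × 1.04 = 1.09 to 1.10 × 1.08 = 1.19. Relaxing the rule removes only the first factor.

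A second run, with 10% noise, CV 50% and a 5 h half-life, agrees. Relaxing the rule lowers the total from 1.57 to 1.42 at 50 ng/mL, from 1.24 to 1.16 at 75, and from 1.11 to 1.06 at 100.

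**The case against.** A reader might infer that the rule does remove the lowest exposures and does bias the low-dose summary. The documents do not support that. Their only dose-normalised free Cmax scales to 39 times the lower limit. The 0.050 L/kg volume comes from that same free-drug curve, so dividing dose by it and calling the result total drug is itself an assumption. The baboon data were taken at 1 mg/kg, so they do not exclude heavy binding at 0.1 mg/kg, but the trigger remains a possibility. The non-zero results come from medians placed at 1.2 to 2 times the lower limit. With a CV of 30% and 10 to 15% noise, inflation at 100 ng/mL is only 1 to 5%. The shortest half-life in the documents is 31.9 h, so the 1.3 h end is pessimistic.

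The very lowest exposures, subjects with every sample below the limit, are lost through the PK population definition and not through this rule. At 60 ng/mL that is the larger effect.

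Nothing is hidden. Excluded subjects stay in the concentration tables and have individual profiles, so a reader can recover their peaks. SAP 6.6 and the Table 11-2 shell already show n for each parameter. PK is secondary and descriptive, and no dose-proportionality test is planned. The rule can also be failed through missed samples, which is not selection on exposure.

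All of this stands, and it limits the point to a small, conditional one. It does not supply a reason for withholding Cmax and Tmax.

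**Conclusion.** The rule is broader than it needs to be: it withholds observed-value parameters for lack of points that only the regression-based ones require. Whether it would affect any subject is unknown. If the median free Cmax in Cohort 1 is 60 to 100 ng/mL, geometric mean Cmax is inflated by about 5 to 19% under the assumed CV, noise and half-lives. At 200 ng/mL the effect is about 1% or less, and at the linearly scaled level it is nil. The documents give no binding constant or predicted human free level with which to choose between these cases. The upward direction applies to Cmax and AUC0-t only. This is a minor improvement, worth making because it is nearly free.

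**What to change.** In SAP 6.5.1:

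- Limit the three-point rule to Kel, T1/2, AUC0-inf, AUC%extrap, AUMC0-inf, CL, MRT and Vss.
- Report Cmax and Tmax for every subject with at least one quantifiable postdose value, and AUC0-t where computable. State that such a subject counts as evaluable for those parameters, because SAP 4.1 also requires an evaluable profile for the parameter summary.
- Reconcile the sentence that keeps these subjects in the concentration tables only with SAP 6.6, which lists excluded subjects in the PK parameter tables.
- Use one term. The SAP says quantifiable and the protocol says detectable.
- Beside the Cohort 1 summary, give the number of actively dosed subjects with no quantifiable sample, so that the remaining upward bias can be judged.

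The cost is a few sentences, plus an entry in SAP section 9 (changes from the protocol-planned analysis). Protocol 12.1 lets the SAP modify planned analyses and reserves a protocol amendment for major changes to the primary endpoints, so none is needed here. The drawback is that some reported Cmax values may rest on one or two samples near the lower limit; a footnote can mark them. If free drug proves to be well above the limit, the edit changes no low-exposure result.

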6.6 Data Summarization and Presentation

All plasma xisomab 3G3 PK concentrations and/or PK parameters descriptive statistics will be generated using SAS® version 9.3 or higher. A concentration table will be presented for pooled placebo samples without descriptive statistics.

The plasma concentrations of xisomab 3G3 will be listed and summarized by treatment and time points for all subjects in the PK Population. Plasma concentrations of xisomab 3G3 will be presented with the same level of precision as received from the bioanalytical laboratory. Summary statistics, including sample size (n), arithmetic mean (Mean), standard deviation (SD), coefficient of variation (CV%), standard error of the mean (SEM), minimum, median, and maximum will be calculated for all nominal concentration time points. Excluded subjects will be included in the concentration listings, but will be excluded from the summary statistics and noted as such in the tables. All BLQ values will be presented as "BLQ" in the concentration listings and footnoted accordingly.

Mean and individual concentration-time profiles will be presented on linear and semilog scales. Linear mean plots will be presented with and without SD.

Plasma xisomab 3G3 PK parameters will be listed and summarized by treatment for all subjects in the PK Population. Pharmacokinetic parameters will be reported to 3 significant figures for individual parameters, with the exception of T1/2 and Tmax, which will be presented with 2 decimal places. Summary statistics (n, Mean, SD, CV%, SEM, minimum, median, maximum, geometric mean [Geom Mean] and geometric CV% [Geom CV%]) will be calculated for plasma xisomab 3G3 PK parameters. Excluded subjects will be listed in the PK parameter tables, but will be excluded from the summary statistics and noted as such in the tables.

The level of precision for each concentration and PK parameter statistic will be presented as follows:

- minimum/maximum: in same precision as in the bioanalytical data for concentrations and same precision for PK parameters presentation
- Mean/median/Geom Mean: in one more level of precision than minimum/maximum
- SD/SEM: in one more level of precision than Mean/median/Geom Mean
- n will be presented as an integer
- CV% and Geom CV% will be presented to the nearest tenth

7. PHARMACODYNAMIC ANALYSIS

7.1 Measurement and Collection Schedule

For all subjects, blood samples for the assessment of aPTT will be collected at predose, and at 0.083, 0.25, 0.5, 1, 3, 8, 24, 72, 120, 168, 216, 336, 504, and 672 hours after xisomab 3G3 start of infusion. Following the 672-hour time point, sample collection for PD assessment will continue every 7 days (\pm 2 days) until aPTT values return within \pm 10% of the baseline value or the normal range.

7.2 Biomarker Method

aPTT will be determined using a light scattering method. This method is a Food and Drug Administration (FDA) approved kit for diagnostic testing and has been validated with respect to accuracy and precision at Celerion, Tempe, Arizona in accordance with the College of American Pathologists (CAP) and the Clinical Laboratory Improvement Amendments (CLIA) requirements for coagulation testing. The reference range for aPTT coagulation time is 23 – 32 seconds.

7.3 Activated Partial Thromboplastin Time

Inhibition of the blood coagulation contact pathway by xisomab 3G3 or its murine precursor, xisomab 14E11, is anticoagulant, as demonstrated by both in vitro and in vivo activated partial thromboplastin time (aPTT) prolongation.

7.4 Activated Partial Thromboplastin Time Values

aPTT values as determined at the collection times and per the biomarker method described in Section 7.1 and Section 7.2, respectively, will be used for the calculation of change from baseline.

7.5 Data Summarization and Presentation

aPTT values will be extracted from the clinical laboratory database and descriptive statistics will be generated using SAS® version 9.3 or higher. A table will be presented for the aPTT change from baseline with descriptive statistics. Change from baseline will be calculated by subtracting the predose aPTT value from the postdose aPTT value at each time point. The mean change from baseline will be calculated using the individual change from baseline values. If change from baseline results in a negative value, this value will be set to '0' for the calculation of the summary statistics.

aPTT values will be listed and summarized by treatment and time points for all subjects in the PD Population. aPTT values will be presented with the same level of precision as received from the clinical laboratory database. Summary statistics, including n, Mean, SD, CV%, SEM, minimum, median, and maximum will be

calculated for all nominal values time points. Excluded subjects will be included in the aPPT values tables, but will be excluded from the summary statistics and noted as such in the tables.

Mean and individual aPTT values-time and change from baseline-time profiles will be presented on linear scale. Linear mean plots will be presented with and without SD.

The level of precision for the aPPT values summary statistic will be presented as follows:

- minimum/maximum: in same precision as in the clinical laboratory database
- Mean/median: in one more level of precision than minimum/maximum
- SD/SEM: in one more level of precision than Mean/median
- n will be presented as an integer
- CV% will be presented to the nearest tenth

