#### 12.1.2 Subjects to Analyze

Safety population: All subjects who received the study drug (active or placebo) will be included in the safety summary.

PK population: All subjects receiving the active drug and having any measurable plasma concentration of study drug will be included in the PK data set. All subjects who comply sufficiently with the protocol and display an evaluable PK profile (e.g., exposure to treatment, availability of measurements and absence of major protocol violations) will be included in the statistical analyses.

PD population: All subjects receiving the study drug (active or placebo) and having any measurable PD data will be included in the PD data set.

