8.4 Clinical Laboratory Tests (Coagulation, Serum Chemistry, Hematology, Urinalysis)

Clinical laboratory tests for serum chemistry, hematology, and urinalysis will be performed at Screen, Check-in (Day -1), Hour 8 postdose on Day 1, Day 2, Day 8, Day 29, and Follow-up (Day 36) or prior to early termination. Bleeding time, which is contained in the hematology panel was performed at Check-in (Day -1), Predose, Hour 1 postdose on Day 1, and Day 2. Clinical laboratory tests for coagulation will be performed at Screen, Check-in (Day -1), and Follow-up (Day 36) or prior to early termination, with additional assessments at Hour 1 postdose on Day 1, Day 2, Day 4, Day 8, and Day 29 for PT and INR.

Out-of-normal range flags will be recorded as follows: high (H) and low (L) for numerical results and did-not-match (*) for categorical results. If a value fails the reference range, it will automatically be compared to a computer clinically significant (CS) range. If the value falls within the computer CS range, it will be noted as "N" for not clinically significant. If the value fails (i.e., fall outside of the CS range) the computer CS range, it will be flagged with a "Y" which prompts the PI to determine how the out-of-range value should be followed using 4 Investigator flags: "N", not clinically significant, "R", requesting a recheck, "^", checking at the next scheduled visit, or "Y", clinically significant. To distinguish the PI flag from the computer CS range flags, the PI flags of "N" and "Y" will be presented as "-" and "+", respectively, in the data listing. Additionally, a derived flag based on a search of the PI comments for a comment of "CS" or "Clinically Significant" will be used. The derived flag will be populated with "+" if the positive clinically significant determination is found in the comments for cases when the PI flag is populated with a "^" or a "R".

Out-of-range values and corresponding recheck results will be listed. Results that are indicated as CS by the PI (either in the PI flag or in PI comments) will be listed in a table.

Bleeding time will be listed with the hematology results and will be included in the hematology out-of-range table but will be summarized with the coagulation results.

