All coagulation results for PD endpoint aPTT will be listed with the clinical laboratory results and included in the out-of-range table, but for the time points outlined in Section 7.1 summaries will not be included in the clinical laboratory summary tables.

For all numeric laboratory values, descriptive statistics will be presented for each laboratory test by assessment time point and treatment (pooled placebo and xisomab 3G3 dose levels). Change from baseline will be summarized in a similar manner. Baseline is defined as the result closest and prior to dose which may include unscheduled or recheck results. This will typically be the result collected on Day -1.

Postdose unscheduled events or rechecks will not be included in summaries. Similarly early termination results will not be included in summaries.

For each laboratory test, a shift table will be developed to compare the frequency of the results at baseline (above normal, normal, or below normal) with the respective postdose results. For urinalysis tests, the categories are normal and outside normal.

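### On its natural reading, the SAP drops a subject without the one Day 1 predose aPTT from all PD summary statistics; this narrows the protocol's PD population undeclared and ignores the check-in aPTT.

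*SAP*

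**What the plan says.** **Baseline.** SAP 7.5: "Change from baseline will be calculated by subtracting the predose aPTT value from the postdose aPTT value at each time point". SAP 7.4 restricts the inputs: aPTT values at the Section 7.1 collection times "will be used for the calculation of change from baseline". SAP 7.1 lists one predose sample and 14 scheduled postdose samples, from 0.083 to 672 hours. Check-in is not among them. The shell for Table 14.2.3.1 likewise heads its change columns as change from Day 1 predose. The PD section says nothing about a missing predose value.

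**Population.** SAP 4.1 requires that subjects "have at least one predose and one postdose quantifiable PD biomarker value". Protocol 12.1.2 is wider: "All subjects receiving the study drug (active or placebo) and having any measurable PD data will be included in the PD data set". SAP Section 9, which lists changes from the protocol-planned analysis, names only the immunogenicity summaries.

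**What exclusion means.** Under SAP 7.5, excluded subjects still appear individually in the aPTT tables but do not count in the summary statistics. SAP 8.4 keeps aPTT at the Section 7.1 times out of the clinical laboratory summary tables, so those values are not summarised elsewhere.

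**Other pre-dose aPTT.** SAP 8.4: "Clinical laboratory tests for coagulation will be performed at Screen, Check-in (Day -1), and Follow-up (Day 36" or before early termination. SAP 7.5 draws the PD aPTT from the same clinical laboratory database. For laboratory safety data, SAP 8.4 sets a different rule: "Baseline is defined as the result closest and prior to dose which may include unscheduled or recheck results". It adds that this is typically the Day -1 result.

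**The concern.** aPTT is the only planned PD marker, and each dose level has 4 active subjects. If the predose tube fails, a rule that reads as requiring that one sample removes the subject from the change summaries and from the raw postdose summaries too. Change from baseline does need a baseline. A mean postdose aPTT at 24 hours does not.

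The data to avoid most of this loss are already planned: every enrolled subject must have an in-range aPTT at check-in. The same SAP treats such a value as an acceptable baseline for laboratory safety data but says nothing of it for the PD marker. A reader of the report would also not learn from Section 9 that the PD population had been narrowed.

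**Working it through.** The plan states no SD, effect size, power or missing-sample rate for aPTT, so there is no planned statistical figure to reproduce. The enrolment count adds up: 6 + 3 × 5 = 21, of whom 4 × 4 = 16 are active and 2 + 3 = 5 placebo.

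**1. Reading the rules together.**

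| Question | Protocol 12.1.2 | SAP 4.1 with 7.1, 7.4, 7.5 | SAP 8.4 (safety laboratory) |
|---|---|---|---|
| Predose value needed to be in the analysis? | No | Yes | Not stated as a condition |
| Which value is baseline? | Not stated | Day 1 predose only | Last result before dose |
| Fallback if Day 1 predose is missing? | Not needed for inclusion | None stated | Yes, by definition |

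SAP 4.1 asks for at least one predose value and Section 7.1 provides exactly one. Without it, the subject is outside the PD population, and SAP 7.5 then excludes that subject from the summary statistics.

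**2. Size of one loss.** Active group: 1/4 = 25%. Pooled placebo: 1/5 = 20%. Going from 4 to 3 subjects raises the standard error of a mean by √(4/3) = 1.155, or 15.5%, at equal SD.

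**3. How often.** The missing rate p is an assumption. P(at least one missing) = 1 − (1 − p)^n.

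| Assumed p | A given group of 4 | Any of 16 active |
|---|---|---|
| 0.5% | 2.0% | 7.7% |
| 1% | 3.9% | 14.9% |
| 2% | 7.8% | 27.6% |
| 5% | 18.5% | 56.0% |

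**4. What averaging check-in and predose would add.** With within-subject SD s, independent errors, and k pre-dose values averaged, SD(change) = s√(1 + 1/k).
- k = 1: 1.414s. k = 2: 1.225s. The reduction is 1 − 1.225/1.414 = 13.4%.
- If the true effect varies between subjects with SD r × s, the ratio of single to averaged is √[(2 + r²)/(1.5 + r²)]: 1.155 at r = 0, 1.095 at r = 1, 1.044 at r = 2 and 1.009 at r = 5.

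So 13.4% is the best case.

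**5. Cost of averaging.** Protocol 10.3.2 requires aPTT within the normal limits at check-in, which Appendix 1 gives as 23-32 s. This truncates the check-in value. At an assumed within-subject CV of 5%, its mean among eligible subjects shifts by about −0.3 s for a true mean of 30 s and −0.7 s for 31 s. It is also drawn on another day, possibly at another time of day.

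**The case against.** **The exclusion depends on a reading.** SAP 4.1 says at least one predose value, not the Day 1 value, and a Day -1 aPTT is arguably predose. This stands as an ambiguity. Sections 7.1 and 7.4 and the table shell point the other way, so the SAP should say which value counts.

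**The loss is hypothetical.** The predose sample is taken during confinement, no missing rate is given, and individual values remain in the tables. All of this stands and keeps the point small.

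**The SAP may modify the protocol.** Protocol 12.1 allows this, and only major changes to the primary endpoints need an amendment. The narrowing is therefore permitted; the fault is that Section 9 does not declare it.

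**A single predose baseline is a normal choice.** It is the planned sample closest to dosing, the PD analysis is descriptive, and raw aPTT is summarised alongside change. This stands. A reader might infer that one baseline value is itself an error that materially inflates noise. The documents do not support that: they give no within-subject SD, and the gain from averaging is at most 13.4% and brings the truncation cost shown above.

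**A reader might also infer that baseline noise makes recovered subjects fail the return-to-baseline rule.** That does not follow. The rule is met by a value within 10% of baseline or within the normal range, and eligible subjects start inside that range. I simulated the full rule for recovered subjects at an assumed 5% CV, conditioning on an in-range check-in value. Failure at one reading was 0.1% with either baseline at a true mean of 27.5 s, and 3.9% (predose only) against 4.0% (mean of two) at 30 s. SAP 7.5 defines a summary-table change and does not govern that visit and sampling rule, so nothing here bears on it.

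**Conclusion.** The point holds as a minor defect in the PD population and the missing-baseline rule. Read together, SAP 4.1, 7.1, 7.4 and 7.5 discard usable postdose aPTT from the summaries when one predose sample fails. This is narrower than Protocol 12.1.2, is not declared in SAP Section 9, and is inconsistent with the baseline rule in SAP 8.4. The consequence is conditional: 25% of a 4-subject dose group for each such failure, at a rate the documents do not give. No test, alpha or power is affected, because none is planned. The conclusion rests on taking predose in SAP 4.1 to mean the Section 7.1 sample. On the looser reading the subject stays in the population, but SAP 7.4 and 7.5 still provide no baseline for the change.

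**What to change.** 1. **SAP 4.1.** Restore the protocol's PD population (any measurable PD data) for raw aPTT summaries. Require a pre-dose aPTT only for change from baseline.
2. **SAP 7.5, with 7.4 to match.** Keep Day 1 predose as the baseline. If it is missing or unquantifiable, use the last aPTT before dosing, normally Day -1, and flag the subject in the tables.
3. **SAP Section 9.** List any departure from Protocol 12.1.2 that remains.
4. **Optional.** Add a sensitivity summary of change using the mean of check-in and Day 1 predose, with the limits on the check-in value stated beside it.

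The first three items are wording changes in the SAP plus a flag in programming; they need no new sample or visit. The cost of the fallback is that the flagged subject's baseline comes from another day and was screened to 23-32 s. Items 1 and 2 prevent the subject loss; only item 4 reduces noise, and the repair does not depend on it.
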